Specific Aim 3, Hypotheses 2a-b (H2a,b). Compared to a general Health and Wellness Intervention, CBT-I will show significant a) decreases in insomnia symptoms (as measured by the ISI) and b) increases in functioning (as measured by the VR-36). Analysis: For the two outcomes for H2a and H2b we will use the mixed model described above. For example, to assess the effect of CBT-I on insomnia severity as measured by variable Y= ISI, the model will be: Y_j=\beta_0+\beta_1 "Y"_1+\beta_2 P"T + β_3 "FU + " β_4 "CBT-I +" β_5 "CBT-I POST + " β_6 "CBTI FU + " e_j , where j = 2, 3 are the PT and FU assessment points respectively, Y1 is the baseline value, and POST, FU, and CBT-I are indicator variables for the PT and FU time-points and the CBT-I intervention condition (versus the control condition). β_5 in the model, equal to the group differences at PT (i.e. treatment effect) and FU, will be tested against the Null hypothesis that that β_5=0. As mentioned above an important out-of-balance covariate and potential confounder could also be included in the model.

Secondary Aims. In secondary analyses, actigraphy outcomes will include the length of time between target bedtime (via sleep log information) and sleep onset (sleep latency), and the number of awakenings after sleep onset. The right-hand-side of the model for Specific Aim 3 will also be used for these outcomes, however the type of longitudinal model may differ. For example, a Poisson or Negative Binomial model using generalized estimating equations (GEE) would likely be a better fit for testing the treatment effect on the count variable, number-of-awakenings.

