Exploratory Aims (EA). We will explore whether clinical and sleep characteristics, physical comorbidities, and other health behaviors: moderate the effect of CBT-I on insomnia and functional outcomes (EA1), and/or improve as a result of participation in CBT-I (EA2). Analysis: For EA1, we would add the three-way interaction terms between the baseline health behavior variable, the CBT-I indicator, and either the PT or FU indicator to estimate differential effects depending on health behavior status or level at PT and FU, respectively. For EA2, we would use a model parallel to the model for H2a, b except the health behavior variable would be the response variable. For a categorical health behavior variable a logit regression model using GEE would be used (e.g. logistic regression). For EA3, if CBT-I improves functioning (H2b), we will explore whether the data indicate that improvement in sleep/insomnia symptoms mediates the effect of CBT-I on functioning. Analysis: We will use standard methods for mediation analysis. For EA4 (durability of effects), we will examine treatment effects at the follow-up visit (i.e. test the significance of β_6) in the comprehensive mixed model specified above for primary aim 3. Here, durability is operationally defined as significantly better outcome at FU (CBT-I vs Control) for those outcomes that were significantly better at PT. This approach (versus testing for no change in effect between PT and FU) allows for the possibility of significantly better outcome at FU even while there is attenuation relative to the PT effect.

Qualitative Interviews. Analysis for Phase 2 (RCT) qualitative interviews will follow the same procedure as those in Phase 1 (Acceptability Trial).

ID: VIEW4E02806052800 Name: v2 Sample Size and Data Analysis

HP-00074686 4/19/22, 11:30 AM

HP-00074686 Sharing of Results V2

Sharing of Results

* Describe whether results (study results or individual subject results, such as results of investigational diagnostic tests, genetic tests, or incidental findings) will be shared with subjects or others (e.g., the subject's primary care physicians) and if so, describe how it will be shared:

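### The printed model for H2a and H2b has seven fixed effects but rank 5, so β_5 and β_6, the coefficients to be tested, are not estimable as written

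*Combined protocol and SAP*

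**What the plan says.** All references are to the section Sample Size and Data Analysis of the combined protocol and SAP.

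- **Specific Aim 3, Hypotheses 2a-b.** In cleaned notation the printed model is Y_j = β_0 + β_1 Y1 + β_2 PT + β_3 FU + β_4 CBT-I + β_5 CBT-I×PT + β_6 CBT-I×FU + e_j, with 0/1 indicators for visit and arm. The response rows are limited: "where j = 2, 3 are the PT and FU assessment points respectively, Y1 is the baseline value". The test is then defined: "β_5 in the model, equal to the group differences at PT (i.e. treatment effect) and FU, will be tested against the Null hypothesis" of zero.
- **Exploratory Aims, EA4.** The follow-up effect is assigned to the other coefficient: "we will examine treatment effects at the follow-up visit (i.e. test the significance of β_6"). Its meaning is an arm difference: "durability is operationally defined as significantly better outcome at FU (CBT-I vs Control"). The alternative is explicitly set aside: "This approach (versus testing for no change in effect between PT and FU").
- **Reuse.** The Secondary Aims paragraph applies the same right-hand side to the actigraphy outcomes. EA1 builds on this model: "we would add the three-way interaction terms between the baseline health behavior variable, the CBT-I indicator" crossed with each visit. The stated purpose of these terms is "to estimate differential effects depending on health behavior status or level at PT and FU, respectively". EA2 reuses the form with a health behaviour as the outcome: "we would use a model parallel to the model for H2a, b".
- **Sample size.** Power is given for an ANCOVA at PT with 22-23 per arm: at least 0.80 for d = 0.60 with a baseline-to-PT correlation of 0.7.

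**The concern.** Two visits and two arms give four cell means. With a common baseline slope that is five quantities, and the printed equation spends seven coefficients on them. Over-parameterisation is harmless if the tested quantity is still defined, but here the tested coefficients are among those that are not.

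The plan also contradicts itself. Reading β_5 as the PT difference and β_6 as the FU difference is right only if β_4 is zero, yet the equation keeps β_4. The sentence on β_5 adds a second meaning by saying that it also covers FU.

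At stake are the tests of both efficacy hypotheses and the durability test. If the equation is fitted literally, what is printed as β_5 depends on which columns the software removes. The documents name neither the software nor a rule.

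**Working it through.** **Inputs.** The seven terms, the 0/1 coding and the restriction to j = 2, 3 come from Specific Aim 3, Hypotheses 2a-b. The POST label in the interaction is read as the PT indicator. The 30 per arm, 22-23 per arm at PT, d and r come from the sample size paragraph. The documents give no alpha, so two-sided 0.05 is assumed.

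**1. The plan's own power figure.** For an ANCOVA at PT, power ≈ Φ( d/√(1−r²) × √(n/2) − 1.96 ). With d = 0.60 and r = 0.7, √(1−0.49) = 0.714 and 0.60/0.714 = 0.840. At n = 22: 0.840 × √11 − 1.96 ≈ 0.83, so power is 0.796.

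| n per arm | normal approximation | noncentral t, 2n−3 df |
|---|---|---|
| 22 | 0.796 | 0.777 |
| 22.5 | 0.805 | 0.786 |
| 23 | 0.813 | 0.795 |

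The stated figure reproduces to within about 2 points. It concerns the arm difference at PT, so that is the contrast the trial was sized for.

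**2. Cell means under the printed equation** (leaving out the baseline term):

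| | PT | FU |
|---|---|---|
| Control | β_0 + β_2 | β_0 + β_3 |
| CBT-I | β_0 + β_2 + β_4 + β_5 | β_0 + β_3 + β_4 + β_6 |

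The arm difference is β_4 + β_5 at PT and β_4 + β_6 at FU. Neither β_5 nor β_6 appears without β_4.

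**3. Rank.** On every row PT + FU = 1 and CBT-I×PT + CBT-I×FU = CBT-I. That is two exact dependencies among seven columns, so the rank is 7 − 2 = 5. Building the matrix for 60 people × 2 visits (120 rows) confirms rank 5, and so does a version with 25% and 35% loss. β_4, β_5 and β_6 are each not estimable; β_4+β_5, β_4+β_6 and β_5−β_6 are. Random effects or a residual covariance structure do not change the rank of the fixed effects. With a log link for the count outcome, the weighted information matrix also has rank 5.

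**4. What the stated null restricts.** Imposing β_5 = 0, or β_6 = 0, on the printed model leaves rank 5 and the residual sum of squares unchanged: 0 df. On the corrected five-column model each restriction takes the rank from 5 to 4: 1 df.

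**5. What could be printed.** For illustration, take a true effect of −4 at both visits. All rows below have identical fitted values.

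| Resolution of the redundancy | β_4 | β_5 | β_6 |
|---|---|---|---|
| FU and CBT-I×FU dropped | −4 | 0 | none |
| PT and CBT-I×PT dropped | −4 | none | 0 |
| PT and CBT-I main effect dropped | none | −4 | −4 |
| Minimum-norm solution | −2.67 | −1.33 | −1.33 |

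Eliminating columns from left to right in the printed order gives the first row, where β_5 is the PT-minus-FU change. Eliminating from right to left removes the intercept and the CBT-I main effect, which gives β_5 and β_6 as intended.

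**6. Which term does the damage.** Removing only β_4 leaves six columns and rank 5, and β_5 and β_6 become estimable. The remaining redundancy touches only β_0, β_2 and β_3.

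**7. EA1.** Adding only the two three-way terms, as the plan states, gives 9 columns and rank 7. The three-way terms are estimable; β_5 and β_6 still are not. If all lower-order moderator terms are added, including moderator × CBT-I, there are 13 columns and rank 9, and the three-way terms are lost too.

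**The case against.** The strongest reply is that the intention is not in doubt. The plan calls β_5 the treatment effect at PT, assigns FU to β_6, defines durability as an arm difference, rejects the change test, and sizes the trial on an ANCOVA at PT. On this view a surplus main effect, in an equation offered as an example, is a notation slip. The bad outcome would also reveal itself: if CBT-I×FU is dropped, β_6 has no estimate and the EA4 test cannot be run. All of that stands, and it is why the harm is conditional. It does not make the printed test valid. A prespecified efficacy test should not depend on a software default, and a missing β_6 need not alert someone who reads only β_5 for H2a and H2b.

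The section also refers back to an earlier description of the mixed model that is not in the available text and might state a constraint. The finding is therefore limited to the equation as printed. Extraction from PDF garbled some symbols, but the coefficients run from β_0 to β_6 in order and the prose names β_5 and β_6 separately.

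Baseline rows might have been intended as responses. That would give rank 7, but the text takes responses only at PT and FU, and β_5 would then be a difference in differences rather than the PT difference.

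On EA1, it is fair to say that the three-way terms survive as the plan words them. The coding caution below applies only if lower-order moderator terms are added.

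**Conclusion.** The point holds. As printed, the model has seven fixed effects and rank 5. The tests of β_5 = 0 (H2a, H2b) and β_6 = 0 (EA4) each have 0 df and address no defined hypothesis. The CBT-I main effect is the term at fault, because it contradicts the plan's own definitions of both coefficients. The result is algebraic and needs no assumption beyond reading POST as the PT indicator and taking responses at PT and FU only.

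The consequence is a risk, not an expected loss. If CBT-I×FU is dropped and β_5 is still read as the PT effect, a benefit of equal size at both visits would be flagged only at the alpha level. Once corrected, each test has 1 df and power at PT is 0.78-0.81 under the plan's inputs and two-sided 0.05. This should be corrected before analysis.

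**What to change.** Do one of the following:

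- Remove the CBT-I main effect and one of intercept, PT or FU, for example Y_j = β_1 Y1 + β_2 PT + β_3 FU + β_5 CBT-I×PT + β_6 CBT-I×FU + e_j (five columns, rank 5, same fit as the printed model).
- Keep any full-rank coding and prespecify the contrasts: the arm difference at PT (β_4+β_5 in the printed notation) for H2a and H2b, and the arm difference at FU (β_4+β_6) for EA4.

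Reword the sentence on β_5 so that β_5 is the PT difference and β_6 the FU difference.

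Carry the corrected right-hand side to the secondary outcomes, EA1 and EA2. In EA1, if lower-order moderator terms are included, use only the by-visit forms (M×PT, M×FU, M×CBT-I×PT, M×CBT-I×FU, where M is the moderator). That gives 9 columns and rank 9, and the two three-way terms are then the differential effects at PT and FU.

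The cost is a few lines of analysis wording, with no extra data or participants.

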(1) In Phase 1 (Acceptability Trial), we will establish the acceptability of CBT-I for Veterans with psychotic disorders and insomnia when delivered using guidelines developed for its use. To do this, we will complete an open trial of CBT-I with six Veterans with psychotic disorders and insomnia (including schizophrenia disorders and bipolar and major depression with psychotic features). Acceptability will be demonstrated by participants' satisfaction with CBT-I and its overall utility, via quantitative assessments and qualitative interviews. Refinements to the guidelines will be made based on this information.

(2) In Phase 2 (RCT), we will test the preliminary efficacy of CBT-I for Veterans with psychotic/bipolar disorders and insomnia when delivered using these refined guidelines. To do this, we will complete a small randomized controlled feasibility and preliminary efficacy trial comparing CBT-I (n=30) to a Health and Wellness control intervention (n=30), evaluating sleep and functioning outcomes. Specifically, feasibility will be demonstrated by adequate rates of recruitment, initial intervention engagement, attendance at intervention sessions, and therapist fidelity. We hypothesize that compared to a general Health and Wellness Intervention, CBT-I will result in significant a) decreases in insomnia symptoms and b) increases in functioning. Regarding exploratory aims, using data collected from the RCT, we will explore whether baseline clinical and sleep characteristics, physical comorbidities, medications, and health behaviors (e.g., smoking, caffeine use) 1) moderate the impact of CBT-I on insomnia and functioning or 2) change as a result of participation in CBT-I, and whether 3) insomnia symptoms mediate the effect of CBT-I on functioning. Lastly, we will (4) preliminarily assess durability of effects of CBT-I on insomnia symptoms and functioning at a 3-month follow-up visit.

* Discuss the research design including but not limited to such issues as: probability of group assignment, potential for subject to be randomized to placebo group, use of control subjects, etc.:

Phase 1 (Acceptability Trial): This phase includes an open acceptability trial and Veteran qualitative interviews. There is no randomization or control group.

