* Describe any additional participant requirements:

ID: VIEW4E0280585B400 Name: v2_Study Procedures

Sample Size and Data Analysis V2

Sample Size and Data Analysis

HP-00074686

If you uploaded a separate research protocol document in the 'Research Protocol' page, cite the applicable section and page numbers from that document in the answer boxes below.

* Provide the rationale and sample size calculations for the proposed target population:

Phase 1 (Acceptability Trial): Due to the estimated rates of insomnia and sleep apnea in prior literature on Veterans with psychotic disorders, we have determined the sample size of 20 to be an appropriate number to attain a final sample size of 6. We determined the sample size of 6 to be feasible for the purpose of an acceptability

Phase 2 (RCT): Due to the estimated rates of insomnia and sleep apnea in prior literature on Veterans with psychotic and bipolar disorders, we have determined the sample size of 190 to be an appropriate number to attain a final sample size of 60. After considering time and resources available with this CDA-2, we believe it will be feasible to randomize 30 individuals per condition, thus the total sample size of 60. With 25% anticipated loss to follow-up at PT, we anticipate outcome assessments at PT for approximately 22-23 participants per condition. We expect 35% loss to follow-up at the follow-up visit, leaving 19-20 per condition). With the anticipated 22-23 per condition with complete data at post-treatment, power is estimated to be at least .80 for detecting between "medium" and "large" effect sizes (d=.60) with the ANCOVA analysis, assuming BL to PT correlation in the response variable is r=0.7. Assuming r=0.6, the detectable effect size increases to d=.67 (with power=.80). Up to 30 participants within the CBT-I condition will be asked to complete the qualitative interview. This will allow us to gain a rich understanding of the variety of experiences participants within the CBT-I condition have had with the treatment.

* Provide the plan for data analysis. Include in the description the types of comparisons that are planned (e.g., comparison of means, comparison of proportions, regressions, analysis of variance, etc.), which is the primary comparison/analysis, and how the analyses proposed will relate to the primary purposes of the study:

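### Does the EA1 moderator analysis need to state that the moderator's lower-order terms are in the model?

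*Combined protocol and SAP*

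**What the plan says.** The Aims/Objectives list, among the exploratory aims, whether baseline characteristics "moderate the impact of CBT-I on insomnia and functioning".

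The model on which EA1 builds is under Specific Aim 3, Hypotheses 2a-b, in Sample Size and Data Analysis. Its right-hand side has an intercept, the baseline outcome, PT, FU, CBT-I, CBT-I x POST and CBT-I x FU. The text defines these: "Y1 is the baseline value, and POST, FU, and CBT-I are indicator variables for the PT and FU time-points". No moderator appears. A closing sentence allows one kind of addition: "As mentioned above an important out-of-balance covariate and potential confounder could also be included in the model".

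Under Exploratory Aims, EA1 is handled in one sentence: "we would add the three-way interaction terms between the baseline health behavior variable, the CBT-I indicator, and either the PT or FU indicator", the purpose being "to estimate differential effects depending on health behavior status or level at PT and FU, respectively". No EA1 equation is printed, and no test or significance level is given for it. The section says neither that the moderator's own terms are included nor that they are left out.

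**The concern.** Read as a complete list of additions, the EA1 sentence gives a model with M x CBT-I x PT and M x CBT-I x FU but without M or M x time. That model forces the outcome to be unrelated to M in the control arm. The three-way coefficient then takes up all of M's relation to outcome in the CBT-I arm, whether or not treatment has anything to do with it.

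Two errors could follow. A variable that predicts ISI or VR-36 equally in both arms could be reported as a moderator of CBT-I. A true moderator whose interaction runs against its prognostic effect could be hidden. The candidates (clinical and sleep characteristics, comorbidities, medications, health behaviors) are variables that could plausibly predict outcome in both arms. The stake is a misleading lead for later research on who benefits.

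**Working it through.** **The plan's own figure.** The documents give no figure for EA1; the nearest is the PT power statement. Inputs from the sample size section: 30 randomized per arm; 25% loss at PT, so 30 x 0.75 = 22.5 per arm ("we anticipate outcome assessments at PT for approximately 22-23 participants per condition"); 35% loss at FU, so 30 x 0.65 = 19.5 ("leaving 19-20 per condition"); baseline-to-PT correlation 0.7; d = 0.60. Two-sided alpha 0.05 is assumed.

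- Residual SD = sqrt(1 - 0.7^2) = sqrt(0.51) = 0.714.
- Standardised difference = 0.60 / 0.714 = 0.840.
- Noncentrality = 0.840 x sqrt(22.5 / 2) = 2.82.
- Power = Phi(2.82 - 1.96) = 0.805 (0.786 by noncentral t).

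For r = 0.6 and d = 0.67 the same steps give 0.802. The stated 0.80 is reproduced, so these inputs are a fair basis for EA1.

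**What the omission would do.** At one visit, with G the CBT-I indicator:

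- Without M: Y = a + b Y1 + c G + d GM. The slope on M is 0 in control and d in CBT-I.
- With M: Y = a + b Y1 + c G + m M + d GM. The slope is m in control and m + d in CBT-I, so d is the between-arm difference.

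Suppose M is prognostic with the same slope m in both arms and there is no moderation. The second model gives d = 0. The first gives d close to m. At an assumed partial correlation of 0.3, m = 0.3 x 0.714 = 0.214 outcome SD per SD of M; the simulated mean coefficient is 0.215.

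**How often M would be flagged.** Simulation at PT: 22 per arm, normal M independent of Y1, treatment effect 0.60, no true moderation, two-sided 5%.

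| Assumed partial r of M with outcome | Without M | With M |
|---|---|---|
| 0 | 5.4% | 4.7% |
| 0.1 | 6.7% | 4.6% |
| 0.2 | 14% | 5.1% |
| 0.3 | 27% | 4.7% |
| 0.4 | 44% | 5.2% |
| 0.5 | 64% | 4.9% |

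A hand check at r = 0.3, using the simulated mean standard error of 0.16: 0.214 / 0.16 = 1.34, and 1 - Phi(1.96 - 1.34) = 0.27. With 19 per arm (FU) the rates without M are 13%, 23% and 57% at r = 0.2, 0.3 and 0.5. A two-visit model (within-person residual correlation 0.6 assumed) gives 14%, 27% and 65% for the PT term, and about 4% to 5% with the lower-order terms.

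If M is the baseline value of the outcome, such as baseline ISI for the ISI outcome, Y1 already supplies its main effect and there is no inflation (5%).

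**Can the text be taken literally at all?** The printed base equation has seven columns. With only two visits, PT + FU equals the intercept column, and CBT-I x POST + CBT-I x FU equals the CBT-I column. That is two exact dependencies, so the rank is 7 - 2 = 5 and the equation cannot be fitted as printed. The text also reads the fifth coefficient as the group difference at PT, which holds only once the separate CBT-I term is dropped. In the full-rank form that matches this reading (PT, FU, Y1, CBT-I x PT, CBT-I x FU), each treatment-by-visit term sits beside its visit term. The direct analogue for EA1 is M x CBT-I x PT beside M x PT, and likewise for FU.

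**The case for a change.** The strongest case for a change is that the plan works at the level of single coefficients, naming the one to test at PT and the one to test at FU. An analyst could therefore take the listed terms as the whole model. The sentence allowing an extra covariate does not rescue it: that covariate is optional and is chosen for imbalance or confounding, not because it is the moderator under study. One added sentence would settle the matter, at the price of two parameters per moderator and a standard error of about 0.22 instead of 0.16 (22 per arm, r = 0.3). The smaller value is no advantage, since it belongs to the wrong quantity.

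The algebra stands, and so does the silence. What does not stand is the step from silence to a wrong analysis. The authors list lower-order terms beside their interactions in the base model, to the point of redundancy, so there is no reason to presume they would drop them in the next step. The purpose they state for EA1 is a difference between arms, and the reduced model does not estimate one. The figures also need care. Each depends on an undocumented partial correlation, and the rates above 40% need 0.4 or more beyond what baseline already explains. The flagging rates assume a test that EA1 does not state: it speaks of estimating, whereas EA4 speaks of testing significance. A masking example can be built (partial r = 0.3 with a true interaction of -0.21, so that the reduced coefficient averages 0.00), but it is tuned to cancel exactly, and even the full model would flag that interaction only about 17% of the time.

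**Conclusion.** No change is needed. The EA1 sentence leaves out detail that an analyst supplies as a matter of routine: a three-way interaction is fitted with the moderator and its product with time, and the stated aim of differential effects calls for that model. The printed base equation has to be completed before it can be fitted, so a strictly literal reading is not available for the base model and should not be reserved for EA1 alone.

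If the terms were nevertheless omitted, the coefficient would be biased by the moderator's prognostic slope, for example 0.21 SD per SD at a partial correlation of 0.3. A two-sided 5% test would then flag it about 7% to 27% of the time at partial correlations of 0.1 to 0.3, instead of about 5%. Those rates rest on an assumed correlation and an assumed alpha, neither of which the plan gives. The consequence would be confined to exploratory leads in a 60-person preliminary-efficacy trial; the primary comparison and its sample size do not depend on EA1.
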